10.1.4 Future Use of Stored Specimens and Data	22
10.1.5 Key Roles and Study Governance	22
10.1.6 Safety Oversight	23
10.1.7 Clinical Monitoring	23
10.1.8 Quality Assurance and Quality Control	23
10.1.9 Data Handling and Record Keeping	23
10.1.10 Protocol Deviations	23
10.1.11 Publication and Data Sharing Policy	24
10.1.12 Conflict of Interest Policy	24
10.2 Additional Considerations	24
10.3 Abbreviations	24
10.4 Protocol Amendment History	25
11 References	28

STATEMENT OF COMPLIANCE

Provide a statement that the trial will be conducted in compliance with the protocol, International Council on Harmonisation Good Clinical Practice (ICH GCP) and applicable state, local and federal regulatory requirements. Each engaged institution must have a current Federal-Wide Assurance (FWA) issued by the Office for Human Research Protections (OHRP) and must provide this protocol and the associated informed consent documents and recruitment materials for review and approval by an appropriate Institutional Review Board (IRB) or Ethics Committee (EC) registered with OHRP. Any amendments to the protocol or consent materials must also be approved before implementation. Select one of the two statements below. If the study is an **intramural** NIH study, use the second statement below:

- 1. The trial will be carried out in accordance with International Council on Harmonisation Good Clinical Practice (ICH GCP) and the following:
 - United States (US) Code of Federal Regulations (CFR) applicable to clinical studies (45 CFR Part 46, 21 CFR Part 50, 21 CFR Part 56, 21 CFR Part 312, and/or 21 CFR Part 812).

National Institutes of Health (NIH)-funded investigators and clinical trial site staff who are responsible for the conduct, management, or oversight of NIH-funded clinical trials have completed Human Subjects Protection and ICH GCP Training. OR

2. The trial will be conducted in accordance with International Council on Harmonisation Good Clinical Practice (ICH GCP), applicable United States (US) Code of Federal Regulations (CFR), and the [specify NIH Institute or Center (IC) [Terms and Conditions of Award. The Principal Investigator will assure that no deviation from, or changes to the protocol will take place without prior agreement from the funding agency and documented approval from the Institutional Review Board (IRB), and the Investigational New Drug (IND) or Investigational Device Exemption (IDE) sponsor, if applicable, except where necessary to eliminate an immediate hazard(s) to the trial participants. All personnel involved in the conduct of this study have completed Human Subjects Protection and ICH GCP Training.

For either option above, the following paragraph would be included:

The protocol, informed consent form(s), recruitment materials, and all participant materials will be submitted to the IRB for review and approval. Approval of both the protocol and the consent form(s) must be obtained before any participant is consented. Any amendment to the protocol will require review and approval by the IRB before the changes are implemented to the study. All changes to the consent form(s) will be IRB approved; a determination will be made regarding whether a new consent needs to be obtained from participants who provided consent, using a previously approved consent form.

1 PROTOCOL SUMMARY

1.1 SYNOPSIS

Title:	HCMR Re-Imaging Study	
Study Description:		
Objectives:	Primary Objective:	To assess the change in biomarkers and CMR parameters including LV mass, maximal wall thickness, and LGE extent from baseline over a minimum of 7 years of follow-up extent in HCM patients who would have been candidates for clinical trials of aficamten.
	Secondary Objectives:	
Endpoints:	Primary Endpoint:	% LGE mass
	ints: Primary Endpoint: % LGE mass Secondary Endpoints: LV mass, end-diastolic vol volume (ESV), stroke volu (EF), and LV mass index (I RV EDV, ESV, SV, EF, EDVI Maximal wall thickness LV and RV longitudinal, ci strain LGE – presence, mass T1 – regional and global Extracellular volume – reg	

Study Population:	Within the HCMR original cohort who have 1. Obstructive HCM and		
	• BMI < 35 kg/m2		
	• LVOT-G at entry as follows:		
	Resting gradient ≥50 mmHg OR Resting gradient ≥30 mmHg and <50 mmHg with post-Valsalva LVOT-G ≥50 mmHg		
	NYHA Class II or III or		
	2. Nonobstructive HCM		
	Same criteria as above except resting LVOT-G is <30mmHg and post- Valsalva gradient <50mm Hg		
	• BMI <40kg/m2		
	• Elevated NT-proBNP > 300 pg/mL at the time of enrollment		
	• LVEF ≥55%		
Phase:	Observational		
Description of Sites/Facilities Enrolling Participants:	Selected from original HCMR sites in the U.S. and U.K.		
Description of Study Intervention:	Observational only. No intervention		
Study Duration:	1 year		
Participant Duration:	One visit		

1.2 SCHEMA

1.3 SCHEDULE OF ACTIVITIES (SOA)

Study visit Day	Informed consent
	Medical history and medication review
	Vital signs
	Brief physical exam
	Cardiac MRI with and without gadolinium contrast
	Blood draw for biomarkers

2 INTRODUCTION

2.1 STUDY RATIONALE

A meta-analysis of 5 pooled studies and 2993 patients followed for a median of 3 years has demonstrated that after adjusting for baseline characteristics, the extent of late gadolinium enhancement (LGE) was associated with SCD (1.36 for every 10% increase in LGE as % of LV mass). HCMR data already show a primary event rate of 4% in patients with >10% LGE, 1.3% in patients with 1-10% LGE, and 0.4% in those without LGE. It is this type of observation that underscores the power of this cohort. Two small studies have shown progression of LGE in patients with HCM, primarily in patients with greater hypertrophy and LGE at baseline and progression is associated with a decline in ejection fraction, heart failure hospitalizations, and arrhythmias.^{7,8}

2.2 BACKGROUND

Hypertrophic cardiomyopathy (HCM) has a prevalence of between 1 in 200 and 1 in 500 in the general population and is the most common monogenic heart disease. It is characterized by unexplained left ventricular hypertrophy (LVH), diffuse and patchy fibrosis, and myofibrillar disarray^{1, 2}. It is an important cause of sudden cardiac death (SCD) in young individuals³. While many patients experience a mild clinical course, cumulative disease burden is considerable and most will experience complications, particularly heart failure (HF) or atrial fibrillation (AF)⁴. Accurately predicting prognosis and stratifying risk are important unmet clinical needs⁵. Risk scores to predict SCD using demographic, clinical, and echocardiographic markers have been developed⁹ and tested¹⁰. However, existing risk scores fail to precisely predict risk. Furthermore, based on current guideline-based risk assessment, most patients will be deemed to be at low or intermediate risk, and yet most events occur in these patients^{10, 11}. Identifying novel risk markers is required to improve upon present models. In addition, updated predictive models that focus on other clinically relevant endpoints that can be intervened upon, e.g. HF and AF, will advance the field and improve patient care. Previously available medical therapy for HCM focuses on symptom palliation and does not alter the natural history, protect against SCD, or prevent the development of AF or HF. However, novel disease-modifying therapies are now available¹². Therefore, creating a new prognostic model will identify patients at increased risk for SCD, AF or HF, and will foster the evaluation of novel therapeutic strategies aimed at altering phenotypic expression and natural history. In turn, this would lead to improved survival and quality of life and reduced healthcare costs in HCM.

Our group has set out to redefine risk markers for critical cardiovascular outcomes in HCM through *HCMR, Novel Markers of Prognosis in Hypertrophic Cardiomyopathy*, U01HL117006-01A1.⁶ In this unique and carefully designed study, we have recruited 2750 patients from 44 sites in 6 countries and collected comprehensive demographic, clinical, imaging, biomarker, and genetic data from each. This is the largest systematic prospective study of this disease performed to date. Recruitment was completed in

2.3 RISK/BENEFIT ASSESSMENT

2.3.1 KNOWN POTENTIAL RISKS

Blood Draw and IV placement

The risk of IV line placement and blood draw are of bruising, bleeding, and local infection. A vagal reaction and fainting due to either procedure is quite rare (<1%).

CMR

CMR uses strong magnetic fields to obtain images. During the switching (slewing) of the magnetic fields, the MR scanner makes loud banging sounds that may cause discomfort to patients being scanned. Earplugs will be provided to minimize this discomfort. In addition, the switching of the magnetic field gradients can, under some circumstances, cause peripheral nerve stimulation, which may be

experienced as a mild twitching reaction in certain muscles. Such effects are rare and the switching rates are kept well below the levels where such effects are known to occur frequently. All magnetic field gradient slewing will be within FDA-approved parameters and have not been reported to have adverse health effects. To generate MR images, radio waves are used that can cause a mild warming sensation similar to exposure to hot weather or tanning on the beach. Body temperature may increase slightly (less than 1°C). The total CMR scanning protocol will be accomplished within 60 minutes. ECG leads or fiber-optic detectors will be placed on the subject's body to obtain a triggering signal for the purpose of cardiac gating. ECG leads under very rare circumstances have caused local skin irritation during MR scans. The technical staff has been trained as per standard-of-care to place leads in such a manner as to avoid such burns. There are risks of IV catheter placement that include tenderness, swelling, warmth at the injection site, extravasation of the contrast agent and, rarely, infection. Should the patient experience any of the above discomfort to an intolerable degree, the CMR examination can and will be stopped at any time upon the request of the subject.

Gadolinium

There are rare reports of allergies to gadolinium. With the use of cyclic gadolinium chelates, nephrogenic systemic fibrosis, which was reported with linear chelates before 2010, is no longer an issue. All of the patients recruited will have received gadolinium with their intake CMR in HCMR and have not had a problem with it. Gadolinium is xx in pregnancy

2.3.2 KNOWN POTENTIAL BENEFITS

There are no definite benefits of participating in this study. However, the patient's physician may receive information from the CMR that may be of benefit in the patient's care.

2.3.3 ASSESSMENT OF POTENTIAL RISKS AND BENEFITS The risks of this study are extremely low as are the potential benefits.

3 OBJECTIVES AND ENDPOINTS

OBJECTIVES	ENDPOINTS	JUSTIFICATION FOR ENDPOINTS
Primary		
To assess the change in LGE extent from baseline over a minimum of 7 years of follow-up extent in HCM patients who would have been candidates for clinical trials of aficamten.	Change in % LGE mass	LGE extent is a risk factor for SCD. The progression of LGE over time is incompletely understood.
Secondary		
To assess the change in CMR parameters including LV mass, volumes, and maximal wall thickness, from baseline over a minimum of 7 years of follow-up extent in HCM patients who would have been candidates for clinical trials of aficamten.	LV mass, end-diastolic volume (EDV), end-systolic volume (ESV), stroke volume (SV), ejection fraction (EF), and LV mass index (I), EDVI, ESVI, SVI RV EDV, ESV, SV, EF, EDVI, ESVI, SV, EF Maximal wall thickness LV and RV longitudinal, circumferential, and radial strain LGE – presence, mass T1 – regional and global Extracellular volume – regional and global LA volume, LAVI, and LA strain	Prior f/u CMR studies in HCM are short-term and with a small n. This would be the largest f/u study to date with the largest n.
Tertiary/Exploratory		
To assess the change in biomarkers from baseline over a minimum of 7 years of follow-up extent in HCM patients who would have been candidates for clinical trials of aficamten.	NTproBNP and hsTNT and change in these measures from baseline	Changes in biomarkers over time are also important to understand in HCM

4 STUDY DESIGN

4.1 OVERALL DESIGN

A total of 314 patients from 9 sites (187 with oHCM, 127 with nHCM) will be approached to consent for re-imaging and repeat blood draw. Patients will be approached by the individual site PI and/or CRC and all studies will be performed at that site. Patients who consent will undergo a repeat CMR with similar a protocol to that performed as per the initial study in 2014-17. The only substitution would be a wideband sequence for LGE imaging in patients with devices, as available.

4.2 SCIENTIFIC RATIONALE FOR STUDY DESIGN

This would represent the largest f/u CMR study to date in HCM and the largest n.

4.3 JUSTIFICATION FOR DOSE

n/a

4.4 END OF STUDY DEFINITION

When the last patient has had a study visit for CMR and blood draw

5 STUDY POPULATION

5.1 INCLUSION CRITERIA

Patients in the original HCMR cohort with:

1) Obstructive HCM

- Males and females between 18 and 65 years of age
- BMI < 35 kg/m2
- LVOT-G at entry as follows:

Resting gradient ≥50 mmHg OR Resting gradient ≥30 mmHg and <50 mmHg with post-Valsalva LVOT-G ≥50 mmHg

• NYHA Class II or III

or

2) Non-obstructive HCM

- Same criteria as above except resting LVOT-G is <30mmHg and post-Valsalva gradient <50mm Hg
- BMI <40kg/m2
- Elevated NT-proBNP > 300 pg/mL at the time of enrollment
- LVEF ≥55%

5.2 EXCLUSION CRITERIA

- Paroxysmal atrial fibrillation or flutter documented prior to entry.
- Paroxysmal or permanent atrial fibrillation requiring rhythm restoring treatment (eg, directcurrent cardioversion, ablation procedure, or antiarrhythmic therapy) ≤6 months prior to entry. (This exclusion does not apply if atrial fibrillation has been treated with anticoagulation and adequately rate-controlled for >6 months.)

HCMR Re-Imaging Study Protocol

- History of syncope or sustained ventricular tachyarrhythmia with exercise within 6 months prior to entry.
- Pregnancy due to potential risk of gadolinium to the fetus
- Patients with a pacemaker that are pacer-dependent as they cannot undergo MRI

5.3 LIFESTYLE CONSIDERATIONS

n/a

5.4 SCREEN FAILURES

Patients who have died or been lost to follow-up since entry into the original study

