9.3 POPULATIONS FOR ANALYSES

All patient data collected

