9.4.2 ANALYSIS OF THE PRIMARY EFFICACY ENDPOINT(S)

Change from baseline to follow-up CMR, echocardiographic and biomarkers will be described by absolute difference (follow-up value minus baseline value) and percent change from baseline((follow-up value – baseline value)/baseline value x 100). Associations with baseline values will be examined.

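### The objective is worded for all aficamten-trial candidates, but the plan yields LGE change only in surviving, re-imaged patients, and its counts of the rest share no common denominator

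*Protocol*

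**What the plan says.** The primary objective in section 3 concerns change in LGE extent over at least 7 years in "HCM patients who would have been candidates for clinical trials of aficamten". It does not mention survival or a completed second scan.

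Most criteria refer back to the original study. Section 5.1 sets "LVOT-G at entry as follows" and takes NT-proBNP at enrolment; the atrial fibrillation and syncope criteria in 5.2 are also timed from entry. Two exclusions in 5.2 depend on the patient's state now: pregnancy, and "Patients with a pacemaker that are pacer-dependent as they cannot undergo MRI".

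Section 5.4 defines screen failures as "Patients who have died or been lost to follow-up since entry into the original study". The analysis population in 9.3 is "All patient data collected". Section 9.4.2 describes change by "absolute difference (follow-up value minus baseline value"), together with percent change.

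Section 4.1 gives 314 patients at 9 sites to be approached. Section 7.3 calls a patient lost after three unanswered calls and a certified letter, promises that such patients will be accounted for, and allows sites to be added if losses are substantial.

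**The concern.** Death and loss after entry are outcomes in patients who met the entry criteria; they are not failures of those criteria. Calling them screen failures takes them out of the cohort that the objective describes.

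The protocol itself gives reason to think that absence may be related to the endpoint. Section 2.1 ties LGE extent to sudden death and states that "progression is associated with a decline in ejection fraction, heart failure hospitalizations, and arrhythmias". Some of those events can end in death, or leave a patient unreachable, unwilling or unable to be scanned.

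Two effects need separating. LGE change at 7 years is not defined in patients who have died, so death restricts the result to survivors without biasing a survivor mean. Among survivors, a second scan that is missing through loss, refusal or inability can bias the mean if those patients changed differently. Adding sites under 7.3 restores the number of scans but leaves this selection in place.

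At stake is a description of natural history that is read as applying to all trial candidates when it describes those who lived, were reached, agreed and could be scanned.

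**Working it through.** **1. The plan's own count.** Section 4.1: 187 oHCM + 127 nHCM = 314, as stated.

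**2. Where each entry-eligible patient ends up.**

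| Patient | Place in the protocol |
|---|---|
| Died since HCMR entry | Screen failure (5.4); 4.1 does not say whether already removed from the 314 |
| Lost since HCMR entry | Screen failure (5.4); same doubt about the 314 |
| No answer to calls and letter | Lost, to be accounted for (7.3); link to the same term in 5.4 not stated |
| Reached, declines | No class |
| Now pacer-dependent or pregnant | Excluded (5.2) |
| Has a device, not pacer-dependent | Kept in (4.1, 8.2) |
| Cannot be scanned for another reason | No class |
| Scanned twice | The only patients with a change value (9.4.2) |

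The rows do not add up to a defined total, and the 314 itself changes if sites are added.

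**3. Bias among survivors.** Let r be the share of survivors re-imaged, D_R the mean change in those re-imaged, and D_N the mean change in survivors not re-imaged.

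- Survivor mean = r·D_R + (1 − r)·D_N
- Bias of the re-imaged mean = D_R − survivor mean = (1 − r)(D_R − D_N)
- Gap needed for a 1-point shift = 1/(1 − r)

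The protocol gives neither r nor any progression figure, so every r and gap here is an assumption. Counts suppose that all 314 are alive.

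| r | Not re-imaged | Gap for a 1-point shift | Bias if D_N − D_R = 2 | Bias if D_N − D_R = −1 |
|---|---|---|---|---|
| 0.5 | 157 | 2.0 | −1.0 | +0.5 |
| 0.7 | 94 | 3.3 | −0.6 | +0.3 |
| 0.9 | 31 | 10.0 | −0.2 | +0.1 |

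Units are LGE percentage points. With no gap the bias is 0 at every r.

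**4. Against sampling error.** In SD units of LGE change, the 95% half-width is 1.96/√n, where n is the number re-imaged.

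| r | n | Half-width | Bias, 0.5 SD gap | Bias, 0.25 SD gap |
|---|---|---|---|---|
| 0.5 | 157 | 0.156 | 0.250 | 0.125 |
| 0.7 | 220 | 0.132 | 0.150 | 0.075 |
| 0.9 | 283 | 0.117 | 0.049 | 0.025 |

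Of the shares shown, a 0.5 SD gap exceeds the half-width at 0.5 and 0.7 but not at 0.9. A 0.25 SD gap stays below it at all three.

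**5. Is a link between LGE and absence plausible?** Section 2.1 reports a "primary event rate of 4% in patients with >10% LGE, 1.3% in patients with 1-10% LGE, and 0.4% in those without LGE". No time unit is given. If cumulative, the ratio of the highest group to the lowest is 4/0.4 = 10. If annual, over 7 years it is (1 − 0.96^7)/(1 − 0.996^7) = 24.9%/2.8% = 9.0, and over 11 years (2014 to 2025) 36.2%/4.3% = 8.4. This shows a gradient by LGE extent only. It cannot size the bias, because the protocol does not say which events prevent a second scan and the rates do not concern progression.

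**The case against.** A reader might infer that the protocol sets no class and no denominator for patients not re-imaged. That goes too far. Section 5.4 names deaths and losses, 7.3 has a working definition of loss and promises accounting, 5.2 names two groups who cannot be scanned, and 4.1 gives 314. The narrower point stands: these pieces are not reconciled and decliners have no class.

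It can also be said that 5.4 and 7.3 are sequential, the first covering loss before this study's contact and the second failure to make contact, and that patients to be approached are naturally those not known to have died. Both readings are reasonable, but the text states neither.

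The objective's 7-year minimum implies living patients. This is fair for death. It does not cover living patients who are lost, decline or cannot be scanned.

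The path from arrhythmia to no scan is narrower than it may look. Patients with devices are kept in unless pacer-dependent, with a wideband LGE sequence where available (4.1) and device handling before and after the scan (8.2). This stands.

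Finally, a flow table, a baseline comparison and a weighted analysis are commonly left to a SAP, which is not shown. Their absence is not the finding. The objective, the screen-failure definition and the number to be approached are protocol content, and those are what need reconciling.

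**Conclusion.** The point holds in this form: the objective is wider than what the plan can estimate, and entry-eligible patients not re-imaged are spread over classes that share no denominator. Followed as written, the plan drops deaths and losses as screen failures and supports a broader conclusion than the data allow. It should be corrected, chiefly by wording and reporting.

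The size is unknown. The break-even figures (a gap of 2.0 to 10 LGE points for a 1-point shift, over re-imaged shares of 50% to 90%) rest on assumed shares. They show that selection could matter at low shares and would need a very large gap at high ones.

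A reader might infer that the planned mean will understate progression. The documents do not support a sign. The section 2.1 associations make dependence on LGE plausible, but refusal and failed contact need not follow LGE, and a gap the other way would overstate progression. Confidence is medium, because the share re-imaged and the LGE change in those missing are not given.

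**What to change.** 1. In 5.4, 7.3 and 9.3, replace the screen-failure label for these patients with one class, *entry-eligible, not re-imaged*, recorded by reason: died, lost, declined, could not be scanned. In 4.1, state whether the 314 is counted before or after known deaths and losses.
2. Report the flow from all entry-eligible HCMR patients at participating sites, including any added later. Compare baseline LGE %, LVEF, NYHA class, age, NT-proBNP and oHCM/nHCM between patients re-imaged and not re-imaged. Section 2.2 says HCMR collected comprehensive baseline data from each patient.
3. Word the section 3 objective and the conclusion as change among surviving, re-imaged patients.
4. As a sensitivity analysis only, weight by the inverse probability of re-imaging. Target living patients who are eligible for a scan, leaving out those pacer-dependent or pregnant under 5.2, who have no chance of a second scan and cannot be represented by weights. Keep the covariates few: at a 90% share only about 31 patients would be missing. State that baseline weights do not correct for selection on progression after baseline.

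The cost is wording in five sections (3, 4.1, 5.4, 7.3, 9.3), a flow table, a baseline comparison and one extra analysis. Vital status may need checking for lost patients. The weighted estimate will be less precise, and the conclusion narrower. Reasons for no second scan are best recorded during recruitment.
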